### PROTOCOL SYNOPSIS

Name of company: CLINUVEL (UK) LTD	Name of finished product: SCENESSE®		Name of active ingredient: Afamelanotide
Title of study : A Proof of Concept, Phase IIa, Open Label Study to Evaluate the Safety and Efficacy of Afamelanotide in Patients with Variegate Porphyria (VP)-related skin disease			
Study number: CUV040		Phase of develo	opment: IIa
Study period: 8 months include	ing the screening	g and follow-up p	eriod.
Objectives:  Primary objective  • Evaluate the impact of a	famelanotide on	the severity of sl	kin disease in patients with VP.

 
Secondary objectives
 
Evaluate the safety and to
 
Evaluate the impact of a
 
		-	
Methodology: This is an 8-month open label study in adult patients with confirmed VP-related skin disease. To determine eligibility for entry  Eligible patients will be enrolled			
Clinical evaluations will be performed by the same Investigator over the course of the study during the Screening period (Day -28 and Day 0) and on Days 28, 56, 84, 112, 140, 168 and 196 or Premature Termination (if applicable).			
The evaluations will include assessments of disease severity using an 11-point Likert-type Visual Analogue Scale (VAS), a 5-point Investigator's Global Assessment (IGA) scale and a clinical global impression of change (CGIC) as well as a count of skin lesions			
A mapping of the skin lesions w	vill be performed	l at the same time	e using digital photography.
The patient will also assess disease severity during the Screening period (Day -28 and Day 0) and on Days 28, 56, 84, 112, 140, 168 and 196 or Premature Termination (if applicable) through a VAS and a patient global impression of change (PGIC). Quality of life will be evaluated at the same time  Outdoors light exposure and trauma will be recorded daily by the patient			
Safety assessments (including laboratory evaluations, review of adverse events) will be carried out at each study visit and in between, if required for safety-related reasons, at the Investigator's discretion.			

14 Dec 2022 Page **3** of **83** 

No. of participants planned: 6  Treatment:
Afamelanotide
Diagnosis and main criteria for entry:

 
To be eligible to enter the study, patients must meet the following inclusion criteria:
 
Male or female patients with a biochemically and/or molecular-genetically confirmed diagnosis of VP.
 
Patients with VP-related skin symptoms.
 


 
Aged 18-70 years.
 
Providing written Informed Consent prior to the performance of any study-specific procedure.
 
Willing and able to comply with the conditions specified in the protocol and study procedures, in the opinion of the Investigator.
 

To be eligible to enter the study, patients must not meet any of the following exclusion criteria :  • Had two or more acute attacks of hepatic porphyria, as defined by the occurrence or acute porphyric symptoms
lasting more than two days, within 12 months prior to the Screening period.

 
Presence of severe hepatic disease
 

14 Dec 2022 Page **4** of **83** 

Test product: Afamelanotide				
Dose:				
Dose:				
Mode of administration:				
Subcutaneous injection				
Reference therapy:				
Not applicable				
Criteria for evaluation:				
Efficacy Endpoints:				
Efficacy of the treatment will be assessed by:				

 
Clinical Global Impression of Change (CGIC)
 
				
• IGA of disease severity using an 11-point VAS (VAS IGA);				
• Static IGA of disease severity on a 5-point scale (5-point IGA);				
• Patient's Global Assessment of disease severity evaluating skin fragility using a VAS;				
Patient Global Impression of Change (PGIC)				
Number of new skin lesions (blisters/wounds)				
as counted by the Investigator and mapped by				
standardised digital photography;				
• Quality of Life,				
Patient records     of outdoors light exposure and trauma.				
Safety and Tolerability Endpoints:				
Safety and tolerability will be assessed by measuring treatment-emergent adverse events (TEAEs)				
(coded as MedDRA Preferred Terms).				
Statistical Methods:				
Efficacy analysis:				
Primary efficacy endpoint:				
• The change in severity				
as measured by the CGIC.				
The null hypothesis is formulated as:				
$H_0$ : there is no change in CGIC score at one or more timepoints after treatment.				
Secondary efficacy endpoints:				
• The change in severity				
as measured by:				
o 5-point IGA;				
o 11-point VAS IGA;				
o The Patient's Global Assessment of disease severity using a VAS;				

 
The Patient Global Impression of Change using PGIC.
 
				

14 Dec 2022 Page 5 of 83

• The change in the number of new skin lesions
counted by the Investigator.
• The change in Quality of Life
• Change in outdoors light exposure over time Trauma events will be tabulated.
All the applied instruments will be analysed using appropriate methods to evaluate their suitability to assess changes in skin disease severity,
The patient-related outcome (PRO) instruments will be assessed
based on the judgement of the patients on their suitability to document their skin disease.
Safety Analyses:
The number of participants with TEAEs will be summarised by MedDRA preferred term and
body system. TEAEs will be further summarised by intensity, seriousness, outcome and relationship to study drug. Participants who prematurely terminate treatment due to adverse events
related to study medication will be summarised

14 Dec 2022 Page **6** of **83** 

#### LIST OF ABBREVIATIONS AND DEFINITION OF TERMS

[figure not shown]
ADR	Adverse drug reaction
AE	Adverse event
AE	Adverse event
RIICC	
β-HCG	Beta Human Chorionic Gonadotropin
CGIC	Clinical Global Impression of Change
CRF	Case report form
GCP	Good Clinical Practice
GGT	Gamma Glutamyl Transferase
HREC	Human Research Ethics Committee
ICH	International Council for Harmonization
IGA	Investigator global assessment
ITT	Intention-to-treat
kg	Kilogram
LPI	Last patient in
LPLV	Last patient last visit
MedDRA	Medical Dictionary for Regulatory Activities
mg	Milligram
mL	Milliliter
PGIC	Patient Global Impression of Change
PPIX	Protoporphyrin IX
111/1	1 Totopotphytini 17x
PRO	Patient reported outcome
	Patient reported outcome
QoL	Quality of life
CADD	Cariana almana dana masatian
SADR	Serious adverse drug reaction
SAE	Serious adverse event

SOM	Study Operating Manual
SUSAR	Suspected unexpected serious adverse reaction
TEAEs	Treatment-emergent adverse events
UK	United Kingdom
VP	Variegate porphyria
WMA	World Medical Association

#### 1.0 ETHICS

#### 1.1 Human Research Ethics Committee (HREC)

An appropriate HREC will approve the protocol and the Participant Information and Informed Consent Form before the study is initiated at each study centre. Documentation of this approval will be provided to the Sponsor and/or the Sponsor's designee. The Investigator(s) will have the following responsibilities:

#### 1.2 Ethical Conduct of the Study

This study will be conducted in accordance with the Declaration of Helsinki (see Appendix 1), its revisions and International Council for Harmonization (ICH) guidelines for Good Clinical Practice (GCP) governing the conduct of studies, and all applicable local regulations.

#### 1.3 Participant Information and Informed Consent

The treating physician will make the initial contact with the patient. Prior to any study specific screening procedures, the Investigator will explain to each participant the nature of the study, its purpose, procedures to be performed, the necessity for withdrawal of prohibited medication, expected duration, and the benefits and risks of study participation. After this explanation and before any study specific screening procedures are performed, the subject must voluntarily sign an informed consent

statement in the presence of a witness, if applicable. The inclusion and exclusion criteria will be reviewed at Days -28 and 0 prior to study medication administration.

#### 1.4 Protocol Amendments

Changes in any portion of this protocol will be documented in the form of a protocol amendment and signed by the appropriate CLINUVEL (UK) LTD personnel and the Investigator(s).

Depending on the requirements of the study centre's HREC and relevant Competent Authority (where applicable), protocol amendments will either need to be submitted for approval or advised by notification. Where formal approval is required, the revision will not be implemented until approval has been obtained.

#### 1.5 Confidentiality

All information provided to the Investigator by the Sponsor, including clinical observations at th
investigative centre, are held strictly confidential and confined to the clinical personnel involved in
conducting the study, under the supervision of the Investigator.

#### 3.0 INTRODUCTION AND STUDY RATIONALE

Variegate porphyria (VP) is a rare autosomal dominant inherited disorder characterised by the deficiency of the mitochondrial enzyme protoporphyrinogen oxidase (PPOX), the penultimate enzyme in the haem biosynthesis pathway. VP presents with phototoxicity, leading to chronic blistering and fragility of sun/light-exposed areas of the skin, acute attacks of neurovisceral symptoms, or both cutaneous and acute symptoms. Manifestations of VP appear typically in adulthood, and rarely before puberty. Although the acute neurovisceral attacks can respond to treatment used for other acute porphyrias, at present there is no effective intervention for the chronic skin symptoms. SCENESSE® (afamelanotide 16mg) was granted marketing authorisation in the European Union in December 2014 and in Australia in October 2020 for the prevention of phototoxicity in adult patients with erythropoietic protoporphyria (EPP) and in the United States in October 2019 to increase pain free light exposure in adult patients with a history of phototoxic reactions from EPP, another cutaneous porphyria. In VP and EPP patients present with phototoxicity due to accumulation of protoporphyrin.

The reported prevalence of VP varies from 0.3 to 2 cases per 100,000 inhabitants but has been reported as more common in the Caucasian South African population (up to 1 in 300 people) due to a founder effect. In Europe, the prevalence varies from 0.32 to 1 cases per 100,000 inhabitants. The occurrence of skin disease in VP patients varies; studies from Finland, France, the UK and Switzerland reported that symptomatic patients had either cutaneous symptoms only, acute attacks only or both acute attacks and cutaneous symptoms.

Phototoxicity in VP leads to chronic fragility and blistering,
The lesions result from sun/light exposure that activates
porphyrins and makes the skin fragile as well as prone to blister formation and damage to the
superficial layers from minor mechanical trauma (e.g. slight knock on the back of the hand). The
subepidermal vesicles, bullae, and erosions crust over and heal slowly When
blisters rupture they may become infected and result in pigmented or, more rarely, depigmented scars.
Pain occurs from the superficial wounds and secondary infections  . Some patients develop

[figure not shown]

With the exception of haem arginate for the treatment of acute attacks, there are no authorised medicinal products for VP, in particular for the prevention of phototoxicity and related skin-manifestations. Current advice for the skin complaints of VP patients includes protective clothing and avoidance of sunlight exposure. Analgesics and antibiotics may be used for treating painful and superimposed infections. Topical steroids have been found to have little or no benefit. Advice regarding the avoidance of exacerbating factors such as some drugs, smoking and excessive alcohol consumption has been shown to be effective in reducing the number of acute neurovisceral attacks in VP, although the effect of such measures on phototoxicity and skin complaints has been limited.

VP and EPP share similar clinical features. In both forms, patients experience phototoxicity and suffer episodes most severely in spring and summer when the atmospheric intensity of light increases. Phototoxicity is due to overproduction and accumulation of protoporphyrin IX (PPIX). Light exposure of the skin will result in activation of protoporphyrin in plasma and in interstitial fluids. The activated porphyrins will induce activated oxygen and reactive oxygen species, which in turn induce

lipid- and DNA damage, damage to macromolecules, degranulation of mast cells, inflammatory reaction and endothelial damage. VP and EPP share very similar histopathological changes, with abnormal superficial dermal vessels which are often tube-like with thickened walls containing periodic acid Schiff (PAS)-positive material. In both forms of porphyria, the histological changes are to be found in light and sun-exposed areas.

Afamelanotide is a potent analogue of  $\alpha$ -MSH which stimulates the production of eumelanin in the skin (epidermis) without the specific cell damage that usually occurs when melanin production is stimulated by UV radiation. Melanin, in the form of eumelanin, is a photoprotective agent. The mechanisms proposed for photoprotection include, but are not limited to, the absorption and scattering of UV light, free radical scavenging and quenching of UV light. There is also increasing evidence that melanogenesis represents a major antioxidant defense mechanism in melanocytes, neutralising the deleterious effects of free radicals and active oxygen species. Eumelanin acts as a neutral density filter and, unlike most sunscreens, reduces all wavelengths of light equally so that the photoprotection provided by epidermal melanin pigmentation is essentially independent of wavelength. Moreover, alpha-MSH signalling induces antioxidative enzymes and improves DNA repair processes.

Afamelanotide 16mg has been shown to be effective in the prevention of phototoxicity in EPP and had obtained marketing authorisation in the European Union and to increase pain free light exposure in adult patients with a history of phototoxic reactions from EPP in the United States for this

indication in adult patients. The results of the clinical trials conducted by CLINUVEL, as well as of one long term observational study and the ongoing post-authorisation pharmacovigilance activities,
confirmed the positive safety profile of afamelanotide to date  .
Due to the lack of an effective therapy as well as due to the rarity of the disease no instrument to
assess VP-related skin manifestations and therapeutic effects of an intervention have been developed
until now. Physician's global assessment tools and patient reported outcomes have been developed in collaboration with expert physicians for use and evaluation in this study  .
The primary endpoint chosen for this study uses the Clinical Global Impression of Change (CGIC)
tool.

	_	

This study aims to extend knowledge of the photoprotective effects of afamelanotide in the cutaneous porphyria patients.

#### 4.0 STUDY OBJECTIVES

#### 4.1 Primary Objective

The primary objective of this study is to evaluate the impact of afamelanotide on the severity of the skin disease in patients with VP.

[figure not shown]
#### 4.2 Secondary Objectives

The secondary objectives of this study are to:

- Evaluate the safety and tolerability of afamelanotide in patients with VP;
- Evaluate the impact of afamelanotide on the quality of life of patients with VP.

#### 5.0 INVESTIGATIONAL PLAN

5.1 Overall Design and Plan of the Study
This is an open label, phase IIa pilot study to be conducted in 6 patients with VP skin disease during
an 8-month period
To determine eligibility for study inclusion,
Eligible patients will be enrolled
and will receive
Clinical evaluations will be performed by the same Investigator over the course of the study during
the Screening period (Day -28 and Day 0) and on Days 28, 56, 84, 112, 140, 168 and 196 or Premature
Termination (if applicable).
The evaluations will include assessments of disease severity using an 11-point Likert-type Visual
Analogue Scale (VAS IGA), a 5-point Investigator's Global Assessment (IGA) scale and a clinical
global impression of change (CGIC) as well as a count of skin lesions
A mapping of the skin lesions will be performed at the same time using digital photography.
The patient will also assess disease severity during the Screening period (Day -28 and Day 0) and on
Days 28, 56, 84, 112, 140, 168 and 196 or Premature Termination (if applicable) through a VAS and
a patient global impression of change (PGIC). Quality of life will be evaluated at the same time
Outdoors light exposure and trauma will be recorded
daily by the patient
Safety assessments (including laboratory evaluations, review of AEs) will be carried out at each study
visit and in between, if required for safety-related reasons, at the Investigator's discretion.

#### 5.2.1 Inclusion Criteria

The participants have to fulfil all of the following *inclusion criteria* for study participation:

- Male or female patients with a biochemically and/or molecular-genetically confirmed diagnosis of VP.
- Patients with VP-related skin symptoms.
- Aged 18-70 years.
- Providing written Informed Consent prior to the performance of any study-specific procedure.
- Willing and able to comply with the conditions specified in the protocol and study procedures, in the opinion of the Investigator.

#### 5.2.2 Exclusion Criteria

To be eligible to enter the study, patients must not meet any of the following exclusion criteria :	

 
Had two or more acute attacks of hepatic porphyria, as defined by the occurrence or acu
 
	ıte
porphyric symptoms lasting more than two days, within 12 months prior to the Screening perior	
Presence of severe hepatic disease	
_	

#### 5.2.3 Patient Recruitment Management

Patients known to the principal investigator to potentially fulfil inclusion criteria, will be contacted and asked for study participation. Please refer to the CUV040 Study Operating Manual (SOM) section 5 for a detailed description of the method for patient recruitment management.

#### 5.2.4 Withdrawals and Replacement of Participants

Patient discontinuation occurs when a patient does not complete the study as required by the study protocol. Participants will be free to discontinue their participation in this trial at any time for any reason. In addition, participants may be withdrawn from the trial at the discretion of the Sponsor, the Investigator or medically qualified nominee. A patient may withdraw for any of, but not limited to, the following reasons:

- Informed consent withdrawn by the patient;
- AE requiring study discontinuation of patient;
- When the Investigator's or nominee's best professional judgment would indicate that it would be in the patient's best interest to be withdrawn;
- Violation of inclusion/exclusion requirements.

The reasons for withdrawal or discontinuation of a patient will be recorded in the patient's CRF as well as in the patient's medical notes. If an AE is the reason for discontinuation, the event must be followed up and documented as described in 5.5.3.2 Safety variables of the protocol. If the patient discontinued for any reason after the enrolment into the study, during the treatment period, a study termination visit, as described in 5.5.1 Description of Study Days of the protocol, should be performed at the time of study discontinuation, or as soon as possible after discontinuation. This visit will be documented in the patient's CRF as well as in the patient's medical notes.

Any patient(s) withdrawn from the trial prior to their completion, for any reason, will not be replaced. Data compiled to the point of discontinuation will be used for 'intent to treat' analysis. Participants deviating any of the inclusion and exclusion criteria will be described as protocol deviators. The way in which protocol deviators will be handled in the statistical analysis is described in the present protocol.

#### 5.3 Study Medication

5.3.1 Description of Study Medication
afamelanotide.
5.3.2 Treatment Group  There is only one treatment group in this study. As such, all patients who satisfy the inclusion/exclusion criteria will be allocated a study subject number and receive afamelanotide. Study subject number allocation will be detailed in the CUV040 SOM.
5.3.3 Dosage and Administration of Study Medication  Afamelanotide will be administered on the designated study days.
5.3.4 Packaging and Labeling of Study Medication  The implant will be packaged in amber glass vials. The label will include information in compliance with the local regulatory requirements for clinical trials / investigational medicinal products.
5.3.5 Storage and Accountability  Study medication will be maintained in a safe and secure (locked, restricted access) location and kept at 2-8°C. The expiry or retest date for each afamelanotide implant will be printed on the label. The Investigator will agree not to supply study drug to any persons other than those enrolled in the study. Current and accurate drug receipts, inventory, accountability and dispensing records will be kept for all study drug in the Pharmacy/Investigator Site File(s), and upon study completion, a final inventory and reconciliation of all study drug will be compiled.

#### 5.3.6 Compliance

Data related to the administration of the study drug will be recorded on the CRF.

#### 5.4 Prior and Concomitant Therapy

#### 5.4.1 Prior Therapy

All subjects will be instructed to report to the Investigator any kind of treatments, prescribed medicines, over-the-counter medications, dietary supplements or nutraceuticals that are being used. Use of any other prior and concomitant therapy which may interfere with the objective of the study,

#### 5.4.2 Concomitant Therapy

The Investigator must be informed as soon as possible about any medication taken from the time of screening until the end of the study and these will be fully documented in the CRF. In the event that a subject has taken a medication which has not been pre-approved, the Investigator will make a decision to continue or discontinue the subject, based whether the medication may interfere with the objectives of the study. These include medications which cause photosensitivity or skin pigmentation.

During the study, contraceptive therapy must not be changed.

#### 5.5 Study Procedures

This will be an outpatient study (see flowchart in Appendix 3).

#### 5.5.1 Description of Study Days

#### **5.5.1.1 Screening Period**

#### Screening

The Screening Visit and related procedures will only occur after the informed consent process is performed and a signed and dated informed consent form has been obtained from the patient. The Investigator will assess eligibility for the study after the following procedures are performed:

-
Visit 2
After patient's eligibility has been confirmed by
the Investigator, the following procedures will be performed:
 

_		
-		
-		
_		
_		
_		
_		

		_
I		
		1

_	
_	
-	
_	
•	

	_
-	
_	
-	
	_
_	
Ī	

5.5.2 Study Procedures Flowchart

Please refer to Appendix 3 for the full study flowchart.

5.5.3 Methods of Assessment

5.5.3.1 Efficacy variables

The efficacy endpoints will be as follows:

#### Primary Efficacy Endpoint

• The change in severity

as measured by the CGIC.

#### Secondary Efficacy Endpoints

•	The ch	ange in severity
		as measured by:
	0	The 5-point IGA
	0	11-point VAS IGA scale;
	0	The Patient Global Impression of Change using PGIC
	0	The Patient's Global Assessment using a VAS.
•	The cl	nange in the number of new skin lesions
		as
	counte	d by the Investigator.
•	The cl	nange in Quality of Life
•	Chang	e in outdoors light exposure over time Trauma events will be tabulated.
A 11 .1	1.	
		d instruments will be analysed using appropriate methods to evaluate their suitability to
assess	cnange	es in skin disease severity,
		The DDO instruments will be assessed based on the judgement of
he not	ients of	The PRO instruments will be assessed based on the judgement of a their suitability to document their skin disease.
пе рап	ients of	t their suitability to document their skin disease.
5.5.3.1	1 C	linical Global Impression of Change (CGIC)
		will be used to assess disease severity changes at Days 28, 56, 84, 112, 140, 168 and
		ature Termination Visit, if applicable.
. 70, 01	1 101110	maio Tommiadon Visit, il applicacio.

_	_	2	1	2	TIACI	$\sim$ $^{\wedge}$
Э.		. 1	. І	.2	VAS I	(tA

An 11-point Likert-type Visual Analogue Scale (VAS IGA) scale will be used to assess disease severity at Days -28, 0, 28, 56, 84, 112, 140, 168 and 196, or Premature Termination Visit, if applicable.

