#### 5.5.3.1.3 5-point IGA

A 5-point Investigator's Global Assessment (IGA) scale will be used to assess disease severity at Days -28, 0, 28, 56, 84, 112, 140, 168 and 196, or Premature Termination Visit, if applicable.

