#### 5.5.3.1.4 Patient Global Impression of Change (PGIC)

A PGIC scale will be used to assess disease severity changes at Days 28, 56, 84, 112, 140, 168 and 196, or Premature Termination Visit, if applicable.

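### Do the two visit lists for CGIC and PGIC, one with Day -28 and Day 0 and one without, call for a change to the plan?

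*Combined protocol and SAP*

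**What the plan says.** The synopsis (Methodology) states: "Clinical evaluations will be performed by the same Investigator over the course of the study during the Screening period (Day -28 and Day 0"); the same sentence then adds the seven later visits, up to Day 196. The next sentences name the 11-point VAS IGA, the 5-point IGA, the CGIC and a lesion count as the content of those evaluations. Section 5.1 repeats this, ending with "global impression of change (CGIC) as well as a count of skin lesions".

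For the patient's own ratings the synopsis says: "The patient will also assess disease severity during the Screening period (Day -28 and Day 0"); the later days are the same, and the instruments are a VAS and the PGIC. Section 5.1 has the same sentence, ending "a patient global impression of change (PGIC). Quality of life will be evaluated at the same time".

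The sections on individual instruments differ. In section 5.5.3.1.1 the CGIC "will be used to assess disease severity changes at Days 28, 56, 84, 112, 140, 168 and" 196. In section 5.5.3.1.4: "A PGIC scale will be used to assess disease severity changes at Days 28, 56, 84, 112, 140, 168 and" 196. Neither mentions Day -28 or Day 0. By contrast, in section 5.5.3.1.3 the 5-point IGA "scale will be used to assess disease severity at Days -28, 0, 28, 56, 84, 112, 140, 168 and 196". Sections 5.5.3.1.2 and 5.5.3.1.5 to 5.5.3.1.8 also start the VAS IGA, patient VAS, photography, lesion count and quality of life at Day -28.

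The primary null hypothesis in the synopsis is that "there is no change in CGIC score at one or more timepoints after treatment".

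**The concern.** CGIC is the primary endpoint, and the visible text gives it two visit lists. A form or database built from the synopsis would ask for two ratings that one built from section 5.5.3.1.1 would not. A change scale at Day -28 is also odd in itself, because no earlier study visit exists to compare with.

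There is a design argument too. Section 5.7.2.1 intends to evaluate whether the instruments are suited to measuring change, and section 3.0 says no instrument existed for this disease. In a single-arm, open-label study, a pre-dose Day 0 rating against Day -28 would be the only CGIC or PGIC reading over an interval without study drug. If the Day 28 start governs, that reading is never taken. It is therefore natural to ask whether the lists should be reconciled by dropping Day -28 and keeping Day 0 as a descriptive check.

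**Working it through.** **Inputs.** Six patients (section 5.7.4). Synopsis and section 5.1: Days -28, 0, 28, 56, 84, 112, 140, 168 and 196, which is 9 visits. Sections 5.5.3.1.1 and 5.5.3.1.4: the last seven of these. Dropout and premature termination visits are ignored. The plan states no figure of its own to reproduce on this point.

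**Step 1: size of the mismatch, per scale.**

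| Schedule | Visits | Ratings in 6 patients | Post-treatment ratings |
|---|---|---|---|
| Synopsis and 5.1 | 9 | 6 × 9 = 54 | 6 × 7 = 42 |
| 5.5.3.1.1 and 5.5.3.1.4 | 7 | 6 × 7 = 42 | 42 |
| Day 0 kept, Day -28 dropped | 8 | 6 × 8 = 48 | 42 |

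The first two rows differ by 54 − 42 = 12 ratings: 6 at Day -28 and 6 at Day 0. The post-treatment column is the same throughout. Keeping Day 0 alone produces a third schedule that matches neither existing list.

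**Step 2: effect on the primary analysis.** The null hypothesis refers to the CGIC after treatment. Neither Day -28 nor pre-dose Day 0 is after treatment, so none of the 12 ratings enters it.

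**Step 3: which list is meant.** Set side by side, the detailed sections follow one pattern. The two scales described as rating *changes* in severity start at Day 28. The three scales rating severity itself (VAS IGA, 5-point IGA, patient VAS) start at Day -28, as do photography, lesion count and quality of life. That split is unlikely to be accidental. The synopsis and section 5.1 are summaries that name all instruments under one list of days.

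**Step 4: what a Day 0 rating could show.** Let *p* be the chance that a patient is rated as changed without study drug. The documents give no value, so a range is assumed. The chance that at least one of six is rated changed is 1 − (1 − *p*)^6:

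- *p* = 0.1: 1 − 0.9^6 = 47%
- *p* = 0.2: 1 − 0.8^6 = 74%
- *p* = 0.3: 1 − 0.7^6 = 88%
- *p* = 0.5: 1 − 0.5^6 = 98%

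Exact (Clopper-Pearson) 95% intervals are 0 to 46% for 0 of 6, where the upper limit is 1 − 0.025^(1/6) = 0.459, and 12 to 88% for 3 of 6. The check could expose frequent untreated change but could not exclude a moderate amount.

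**Step 5: comparability.** A Day 0 rating would refer to Day -28 over 28 days. If later ratings refer to the start of treatment, they span up to 196 days. The two could be neither subtracted nor compared directly.

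Season differs as well. Section 3.0 says symptoms are worst in spring and summer. If the March to June 2023 accrual dates in section 7.0 refer to Day -28, Day 0 falls between 29 March and 28 July 2023, and Day 196 between 11 October 2023 and 9 February 2024. The Day 0 rating would say nothing about seasonal drift over that later period.

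**The case for a change.** The best case for acting has two parts.

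First, the contradiction is visible and concerns the primary instrument. The PGIC half is one complete sentence, so hidden text is unlikely to supply an exception. This stands. The CGIC half is less certain, because the public text has a gap straight after the lesion count and a qualifier may be lost there. But a reader who has both places will follow the section that defines each instrument, and either choice leaves the same post-treatment data.

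Second, the severity scales at Day -28 and Day 0 show whether the *patient* is stable before dosing. They do not show whether a *change scale* reports change when no study drug has been given. That is also correct, and the extra rating would be cheap, at a visit already scheduled. Against it, drift before treatment is already recorded on five measures and in photographs. The rating would support no test and no adjustment, it would not address expectation under open-label treatment, and no decision has been named that would turn on it.

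Its feasibility also depends on the reference period printed on the CGIC and PGIC forms (Appendices 4 and 7), which the public copy does not show. If the forms refer to the start of treatment, a Day 0 rating by the same method would be impossible. If they refer to a pre-study state, a Day -28 rating would be possible after all. Experienced statisticians could reasonably differ on whether to add the rating, so its absence is not a fault in the plan.

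**Conclusion.** The two lists do conflict, by exactly Day -28 and Day 0: 12 of 54 ratings per scale, all before treatment. The conflict is a clerical slip in the summary passages. The instrument sections give a coherent schedule with both change scales starting at Day 28, and following it costs the analysis nothing, because the 42 post-treatment ratings and the primary hypothesis are the same either way. Bringing the summary wording into line would be tidying and would alter no result. A pre-dose Day 0 change rating is an optional addition of small value in six patients (0 of 6 is compatible with anything up to 46%), so leaving it out is a fair choice.

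This rests on two assumptions: that the instrument sections govern, and that the Appendix 3 flow chart, the visit procedures and the rating forms, none of which is visible in the public copy, do not say otherwise. If they do, the count of pre-treatment ratings changes, but the schedule of post-treatment ratings and the primary hypothesis do not.
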